Correlation of CAC to IR: Presence of CAC and progression of CAC were found to correlate inversely with GIR and directly with NEFA levels during clamp stage 2 for both T1D and non-DM groups after adjustment for age (Table 4)⁴⁷. By logistic regression analysis the odds ratio for existence of CAC is 0.45 for every 1 SD increase in GIR and 2.4 for every 1 SD increase in stage 2 NEFA levels. These data support the underlying rationale for studying IR in T1D, indicating that as in other populations, IR is a correlate and predictor of CVD.

Increased vascular stiffness in T1D correlates with an estimate of IR:

Measurement of pulse wave augmentation index (AI), a measure of arterial stiffness, has been performed in a large subset of the CACTI population (n=385). After adjustment for age and gender, AI remains significantly greater in T1D than non-DM subjects (mean, 95% confidence interval: 19.5, 18.2 - 20.7 vs. 16.6, 15.4 - 17.7; $p=0.0011$). When estimated glucose disposal calculated by the Pittsburgh prediction equation³⁰ is added to the model the effect of T1D is completely lost, suggesting that the increased arterial stiffness seen in T1D may be explained by their increased IR.

[figure not shown]

Figure 2 §Least square means adjusted for age, BMI (kg/m²), gender, starting glucose concentration, and time point insulin level. * $p < 0.05$ for difference by diabetes in men; # by diabetes in women; † $p < 0.05$ for sex difference in DM; ‡ in nonDM.

	Spearman correlation coefficient IR vs CAC volume for total cohort (n=87)		
	V3 CAC volume	Baseline to V3 change in CAC	V2 to V3 change in CAC
GIR (mg/kg FFM/min)	-0.42 ($p<0.0001$)	-0.41 ($p<0.0001$)	-0.24 ($p=0.028$)
Stage 2 NEFA level (μ M)	0.41 ($p<0.0001$)	0.40 ($p=0.0001$)	0.27 ($p=0.01$)
		Logistic regression analysis Odds ratio for any CAC at visit 3 (n=87)	
		OR per 1 SD change	p-value
GIR (mg/kg FFM/min)	0.45 (0.22-0.93)	0.03	
Stage 2 NEFA level(μ M)	2.40 (1.08-5.32)	0.032	

Table 4 : IR predicts CAC and correlates with CAC volume

IV. Research Methods

A. Outcome Measure(s):

- Primary outcomes (post each intervention period (placebo vs Metformin): (1) Glucose infusion rate (GIR) during high insulin infusion in hyperinsulinemic euglycemic clamps, (2) Endothelial function measured as percent flow-mediated brachial artery dilation (FMD),

- Secondary (confirmatory and exploratory) outcomes (post each intervention period (placebo vs metformin):
 - NEFA suppression during clamp stage 2,

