 - arterial stiffness (PWV and AI),
 - CGM measures of hyperglycemia, hypoglycemia, and glycemic variability for one week prior to each clamp,
 - Metabolic (NEFA, lipids, insulin, glucose), inflammatory (IL-6, TNF- α , hsCRP, adiponectin), thrombotic (PAI-1), oxidative stress (urinary isoprostanate, TBARs), and endothelial (ICAM, endothelin-1) markers at baseline each study day,
 - Counter-regulatory hormones (cortisol, growth hormone, glucagon, and catecholamines prior to each clamp,
 - Respiratory quotient at baseline and after low dose insulin infusion,
 - Heart rate variability,
 - Mitochondrial content (DNA and electron transport chain complexes),
 - Mitochondrial function (carbohydrate and lipid oxidation, max state 3 O₂ consumption, uncoupled O₂ consumption),
 - Mitochondrial state 3 O₂ consumption,
 - Mitochondrial oxidant generation (H₂O₂ production, glutathione redox state), and
 - Mitochondrial ATP production/ADP depletion by 31P-MRS.

[figure not shown]
B. Description of Population to be Enrolled: Study Design and Research Methods

Hypotheses: Metformin will improve (1) insulin action, (2) vascular function and compliance, and (3) mitochondrial function and oxidant generation in T1D subjects supporting a therapeutic role for metformin in T1D management, including CVD risk management.

Specific Aims: **Specific Aim 1:** Determine the effect of metformin on IR in T1D. **Specific Aim 2:** Determine the effect of metformin on vascular correlates of IR. **Specific Aim 3:** Determine the effect of metformin on mitochondrial function and oxidant generation.

Overall research plan: I propose to address these hypotheses and aims with a single-blinded, fixed-order, placebo-controlled cross-over design study in T1D subjects. The intervention will consist of 6 weeks of treatment with metformin, separated from the placebo period by a \geq 2 weeks washout period. The fixed order is needed because we and others have found persistent residual effects from metformin treatment, and the necessary washout period is not known. Metformin has been studied to a limited degree in T1D, primarily in terms of glycemic control. It has been found to be safe and well-tolerated in these studies (Vella) and the proposed dose and duration have precedent in the literature. [name] at this institution has performed a study using metformin in T1D youth. From his contact with the FDA, an IND is not required for this study.

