Surrogate measures of CVD risk: The proposed study uses known sequelae of IR as surrogate markers for longterm cardiovascular damage (Figure 3)⁴⁸. The proposed markers well supported in the literature as sequelae of IR, as mediators and/or predictors of CVD outcomes or CVD mortality, and as measures capable response to short-term interventions.

Endothelial function: It is generally accepted and widely supported in the literature that IR states are accompanied by impaired endothelial function^{49, 50} and that endothelial dysfunction responds to acute manipulations⁵¹ and correlates with CVD risk and outcomes⁵². **Arterial stiffness and central blood pressure:** Central artery stiffness is increased in obesity and diabetes, including T1D, and correlates with IR in T2D and non-DM populations⁵³. Arterial stiffness⁵⁴ correlates with CVD mortality and central arterial blood pressure measured by applanation tonometry appears to be a stronger predictor of CVD than overall blood pressure⁵⁵. Arterial stiffness is increased with just two hours of physiological-range NEFA elevation by lipid infusion and is thus a dynamic vascular measure⁵⁶. **Mitochondrial function and oxidant generation:** Though proposed as a mechanism for IR, most data supports mitochondrial dysfunction and resulting oxidant generation as a sequela of IR and a contributor to complications thereof^{57, 58}. NO has recently been shown to play a key role in mitochondrial biogenesis and function suggesting that vascular IR may be a contributor to this mitochondrial dysfunction⁵⁹. **Sympathetic nervous system (SNS) activation:** IR states are accompanied by SNS activation and considerable evidence supports this as a contributor to CVD risk⁶⁰. NO plays a key role in modulating SNS activity suggesting again that vascular IR may play a role in SNS activation^{61, 62}.

Recruitment: 100 eligible T1D subjects (50% male) will be enrolled for this study with the goal of starting 40 subjects in order to complete both arms in 30 T1D subjects (see power analysis). Recruitment will be by IRB approved flyers and email advertisement, and through clinical providers at the University Hospital and Barbara Davis Institute Endocrinology clinics. Subjects will also be recruited from the CACTI cohort (>1100

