microalbumin) will be performed to screen for exclusionary medical conditions. During study visits blood sampling will be done at baseline (AM of study day) for measurement of metabolic markers (NEFA, triglycerides, glycerol, glucose, lactate, and insulin levels), endothelial and inflammatory markers (endothelin 1, interleukin 6, TNF- α , and hsCRP) and a prothrombotic marker (PAI-1); and during the clamp as specified above.

Endothelial function: By brachial artery flow-mediated dilation (FMD) methodology described by Celermajer^{64, 65}. FMD is measured using B-mode ultrasound images, with the use of a GE VingMed Vivid Five ultrasound system and a 10.0-mHz linear-array transducer. The brachial artery is scanned in longitudinal sections 2-15 cm above the elbow. When a satisfactory transducer position is found, the skin is marked and the arm left in the same position throughout the study. Increased flow is then induced by inflation of a pneumatic tourniquet around the forearm proximal to the scan site to a pressure of 200mmHg for 5 minutes, followed by release. Doppler measures of blood velocity and diameter will be done at baseline and the first 10 seconds post cuff release. Hyperemic response is then measured for two minutes after cuff deflation. Analysis of recordings will be performed using the CTRC vascular software package available in the Leprino Building. FMD is calculated and adjusted for hyperemic flow velocity.

Arterial stiffness: Arterial stiffness will be assessed non-invasively by TMSphygmocor BPAS 1device (Atcor Medical) applanation tonometry measurement of augmentation index (AI) and pulse wave velocity (PWV)^{66, 67 68}. Three electrocardiography leads are placed with removable adhesive on the chest wall, for the purpose of timing systole. A small metal tonometer is sequentially placed on the skin overlying the radial, femoral and carotid arteries. The anterior wall of the artery is flattened, as with palpation of a pulse. The tonometer non-invasively measures the pressure pulse waveform at each of these sites and correlates this with ECG data and the distance between the femoral artery and carotid artery sites to determine pulse wave velocity.

Echocardiogram: Standard 2-D and Doppler echocardiography with images adequate for speckle tracking analysis will be performed during the inpatient study visits to assess cardiac function.

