Sympathetic/parasympathetic balance: Respiratory heart rate variability by standard methods⁶⁰. Study participants will undergo supine resting electrocardiogram (ECG) recording for 5 minutes early in visits in a quiet room, with a stable room temperature. Participants will be asked to relax but not fall asleep and to breathe normally and remain still without talking during the ECG recording. Following the resting ECG, a second supine ECG will be recorded while study participants take in a deep breath for 10s. The ECG recordings will be transmitted electronically to the Epidemiological Cardiology Research Center (EPICARE) Center (Wake Forest University School of Medicine, Winston-Salem, NC) for analysis, interpretation, and calculation of heart rate variability. The SD of consecutive RR intervals of the entire record in Lead II will be used as a measure of overall HRV. In addition, autoregressive power spectral analysis will be used to determine the spectral power in the following bands: high frequency (HF, 0.15–0.45 Hz, reflects parasympathetic outflow), low frequency (LF, 0.04–0.15 Hz, reflects both sympathetic and parasympathetic outflow), and very low frequency (0.01–0.04 Hz). LF/HF and HF normalized to total power will be analyzed as measures of sympathetic and parasympathetic outflow, respectively.

Indirect calorimetry: For measurement of RQ fasting and during low infusion rate to assess insulin response of shift from fat to carbohydrate metabolism.

Muscle biopsy: Vastus lateralis muscle biopsies by the Bergstrom technique⁶⁹. Samples will be analyzed fresh for respirometry and H₂O₂ production; others will be flash frozen in liquid N₂ and stored at - 80° for PCR, glutathione assays, and immunoblotting. [name] does these biopsies regularly and will assist initially and train the PI in performance of these biopsies.

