Statistical Analysis Plan: In order to test the effects of metformin on insulin sensitivity, vascular function and compliance (FMD, PWV, AI, and post-occlusion blood flow) in T1D, we will measure insulin sensitivity and vascular parameters in 30 T1D (50% men) after six weeks of metformin and six weeks of placebo in a fixed-order, single-blind cross-over design study. The effect of metformin treatment on insulin sensitivity and vascular function will be assessed by comparing fasting measures at post each period of treatment within study participants using paired t-tests.

CGM data for the final week of the intervention will be analyzed for mean glucose, %>180, %<60, and SD (measure of glycemic variability). Initial analysis will be by paired t-test to assess for differences between the two intervention periods. The impact on insulin sensitivity of CGM parameters that differ between intervention periods will be investigated using a repeated measures mixed effects model with CGM parameters included as time-varying covariates.

Secondary measures (inflammatory, thrombotic, oxidative stress, and endothelial markers, metabolic parameters, autonomic function, and biopsy assays) will be similarly compared. Further, the association of secondary outcomes with vascular function will be analyzed using Pearson correlation coefficients and multivariate linear regression. I plan to use all of the variables that appear to correlate individually in the multiple regression analysis as an exploratory exercise. I recognize that an n of 30 is inadequate to power this model, but will perform this analysis as an exploratory, hypothesis generating exercise. As a further exploratory approach, I plan to use "best 3" and "best 4" best subset regression analyses to identify the variables that are most strongly associated with insulin sensitivity and endothelial function. Subgroup analyses will also be conducted to examine whether metformin affects vascular function in men and women to the same degree.

Power and Sample Size: Power analysis and sample size are based on expected changes from the literature for the primary outcomes FMD and insulin sensitivity.

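### Augmentation index is compared between periods with no stated handling of heart rate, so in a fixed-order design a heart-rate change between admissions cannot be separated from a metformin effect on it

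*Combined protocol and SAP*

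**What the plan says.** Section IV.A lists "arterial stiffness (PWV and AI") among the secondary outcomes, with no heart-rate qualifier. The Arterial stiffness paragraph of section IV.D describes "applanation tonometry measurement of augmentation index (AI) and pulse wave velocity (PWV"). It adds: "Three electrocardiography leads are placed with removable adhesive on the chest wall, for the purpose of timing systole". The paragraph on sympathetic/parasympathetic balance in the same section provides a separate ECG: "Study participants will undergo supine resting electrocardiogram (ECG) recording for 5 minutes early in visits".

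The Statistical Analysis Plan in section IV.F names the vascular set as "vascular function and compliance (FMD, PWV, AI, and post-occlusion blood flow) in T1D" and gives the method: "vascular function will be assessed by comparing fasting measures at post each period of treatment within study participants using paired t-tests". Its one covariate model for the treatment comparison puts CGM parameters into the analysis of insulin sensitivity. Heart rate does not appear in it. By contrast, section IV.D does state a physiological adjustment for FMD, namely for the velocity of the hyperaemic flow.

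The Study design text in section IV.B fixes the order as placebo then metformin for all subjects.

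**The concern.** AI measures how much the reflected wave adds to the central pulse during systole. It therefore varies with the length of systole, and so with heart rate, at unchanged wall stiffness: in general a higher heart rate gives a lower AI. This is general measurement knowledge; the protocol does not state it.

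The fixed order makes this matter more here than in an ordinary cross-over. With randomised order, a heart-rate drift from first to second admission (for example, habituation to an overnight stay with cannulation, biopsy and clamp) would be balanced between treatments. Here it falls wholly on the metformin contrast, even if the drug has no effect on heart rate. A rise in heart rate could then pass as improved compliance, and a fall could hide a true improvement. Arterial compliance is one of the four domains in the overall hypothesis, so an AI result is likely to be read as evidence about stiffness.

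**Working it through.** **The plan's own figures.** No power, sample size or alpha is stated for AI, so there is no AI design figure to reproduce. I checked the calculation against the two powers stated in Power and Sample Size, using a paired t-test (noncentral t, two-sided 0.05, n = 30):

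- Insulin sensitivity: difference 0.5, SD of the difference 1, gives 75.4% (stated 75%).
- FMD: difference 1.5, SD of the difference √(2.1² + 1.9²) = 2.83, gives 80.1% (stated 80%).

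Both reproduce, so the same method is used below.

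**Inputs from the documents.** There are 30 paired completers. The only AI contrast is in section III: "After adjustment for age and gender, AI remains significantly greater in T1D than non-DM subjects", with means of 19.5 and 16.6, a difference of 2.9 points. That difference is used only as a yardstick. The plan does not set it as a target.

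**Assumed inputs, because the documents give none.**

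- Slope: AI lower by 0.2 to 0.6 points per 1 bpm higher.
- Mean heart-rate change between admissions: 3 to 5 bpm.
- SD of the within-subject AI difference: 6 points, with 4 and 8 as alternatives.

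**Step 1, size of the artefact.** Artefact = slope × heart-rate change.

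- Smallest: 0.2 × 3 = 0.6 points, which is 0.6/2.9 = 21% of the yardstick.
- Middle: 0.4 × 3 = 1.2 points (41%) and 0.4 × 5 = 2.0 points (69%).
- Largest: 0.6 × 5 = 3.0 points (103%).

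**Step 2, chance that the planned test is significant when stiffness has not changed.** The noncentrality is artefact × √30 / SD and the critical value is t(29) = 2.045. For example, 2.0 × 5.477 / 6 = 1.83 gives 42%.

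| Artefact (points) | SD 4 | SD 6 | SD 8 |
|---|---|---|---|
| 0.6 | 13% | 8% | 7% |
| 1.2 | 36% | 19% | 13% |
| 2.0 | 75% | 42% | 26% |

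The nominal rate is 5%. The test is two-sided, so the table applies to a heart-rate change in either direction.

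**Step 3, the opposite case.** Suppose a true 2.9-point fall in AI is opposed by an artefact. At SD 6, power is 73% with no artefact. It falls to 53%, 32% or 13% when the remaining difference is 2.9 − 0.6 = 2.3, 2.9 − 1.2 = 1.7 or 2.9 − 2.0 = 0.9 points.

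**The case against.** The strongest reply is that nothing here is quantified by the trial. Slope, heart-rate shift and SD are all assumed, and at the low end the damage is small: a 0.6-point artefact raises the false-positive rate only to 8% at SD 6 and 7% at SD 8. AI is one of many secondary outcomes that the plan calls confirmatory or hypothesis generating, and PWV is measured beside it. The overnight admission, overnight insulin drip, standard diet and rescheduling for illness reduce some sources of heart-rate variation. All of this stands, and it limits the weight of the point. None of it removes a systematic difference between first and second admission.

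It is also fair that the plan never says which AI index it will analyse. That raw AI is meant is a reading of its silence. But an undefined index leaves the choice between raw and standardised values open until the data are in.

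Two stronger readings are tempting and should be resisted:

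- A reader might infer that the trial expects metformin to change heart rate, because section IV.B says "IR states are accompanied by SNS activation and considerable evidence supports this as a contributor to CVD risk" and heart rate variability is an outcome. The documents make no such prediction. The overall hypothesis does not name sympathetic tone, the planned variability indices are not mean heart rate, and section IV.E lists sympathetic activation among the mechanisms to explore if GIR or vascular measures do not change.
- A reader might extend the argument to PWV and blood pressure. The documents give no figure from which to size that, and the tonometry methods do not describe recording mean arterial pressure with the reading.

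**Conclusion.** The point holds as a gap in a secondary analysis. As written, the plan cannot tell an AI change due to arterial stiffness from one due to a heart-rate difference between the admissions, and the fixed order means that nothing in the design balances such a difference. This conclusion needs only the general dependence of AI on heart rate and the fixed sequence. It does not need metformin to act on heart rate.

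The size is conditional. It is 0.6–3.0 points under 0.2–0.6 points per bpm and 3–5 bpm. For artefacts of 0.6 to 2.0 points at an assumed paired SD of 6, the false-positive rate is 8% to 42%. If the mean heart-rate shift is near zero, there is little bias.

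A reader might also infer that handling heart rate would pay for itself in precision. The documents give neither the slope nor the heart-rate SD needed to show this, so the case rests on interpretation alone. The two primary outcomes and the sample size are not touched.

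**What to change.** In the Arterial stiffness paragraph of section IV.D, state that heart rate from the tonometry ECG is kept with each reading, and name the AI index to be analysed. In the Statistical Analysis Plan, pre-specify AI standardised to a fixed heart rate (75 bpm), compared by the same paired t-test. Report it beside raw AI and the mean within-subject heart-rate difference. Add that an AI change will be attributed to arterial stiffness only if the standardised result agrees with the raw one.

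The cost is plan wording and the storage of one more value per reading. ECG leads are already placed for tonometry, but the documents do not say that heart rate is saved, so this should be confirmed. The downside is that standardised AI leaves out any drug effect that acts through heart rate. It should therefore supplement raw AI and not replace it. Standardisation removes only the heart-rate part of a visit-order effect; any other drift between the two admissions stays confounded with metformin.

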Hypothesis 2: Metformin will improve vascular and mitochondrial measures in T1D subjects supporting a role for IR in vascular disease in T1D. Approach: T1D subjects (n=30) will have placebo and then metformin added to their usual insulin regimen for six weeks as in SA#1. Vascular function will be measured by flow-mediated dilation, overall vascular reactivity by venous plethysmography, and arterial compliance by applanation tonometry (Sphygmacor Vx device) and brachial artery distensibility (DynaPulse). Heart rate variability will be assessed as a measure of cardiac sympathetic nervous system balance. Mitochondrial function will be assayed by respirometry (Oroboros Oxygraph O2K) and oxidant generation by Amplex Red (Invitrogen) in muscle biopsy samples. A subset of subjects (n=10) will also have mitochondrial function assessed by 31P-MRS to measure ATP production.

The results of the above study may support an important new therapeutic approach to T1D and thus have the potential to significantly alter the future of cardiovascular disease risk management and mortality in T1D.

II. Background and Significance:

[figure not shown]
The prevalence of cardiovascular disease (CVD) is increased in type 1 diabetes (T1D) at least as much as in T2D, and CVD remains the leading cause of death in T1D despite improvement in glycemic control and aggressive management of standard CVD risk factors¹⁻⁵. Recent studies suggest that we have reached the limit of our ability to safely control glucose levels with currently available therapy⁶⁻⁸. In addition, we and

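### LF/HF is to be analysed as sympathetic outflow, although by the plan's own band definitions it reflects the balance between the two branches

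*Combined protocol and SAP*

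**What the plan says.** The spectral measures are defined in Section IV.D, in the paragraph headed "Sympathetic/parasympathetic balance: Respiratory heart rate variability by standard methods". It gives each frequency band a meaning:

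- HF (0.15–0.45 Hz): "reflects parasympathetic outflow".
- LF (0.04–0.15 Hz): "reflects both sympathetic and parasympathetic outflow".
- A third band, "and very low frequency" (VLF, 0.01–0.04 Hz), is assigned to neither branch.

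The next sentence sets the interpretation: "LF/HF and HF normalized to total power will be analyzed as measures of sympathetic and parasympathetic outflow, respectively". Total power is not defined, so it is unclear whether VLF counts in it. The SD of RR intervals is kept as the overall measure of variability.

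Elsewhere the plan is more cautious. Aim 2 in Section I says "Heart rate variability will be assessed as a measure of cardiac sympathetic nervous system balance", and the paragraph heading in IV.D also speaks of balance. Section IV.A lists heart rate variability among the secondary outcomes. Section IV.F states the comparison: "Secondary measures (inflammatory, thrombotic, oxidative stress, and endothelial markers, metabolic parameters, autonomic function, and biopsy assays) will be similarly compared", which refers back to the paired t-tests.

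**The concern.** Two adjacent sentences do not fit together. If LF carries both branches and HF carries one, then LF/HF has a mixed numerator and a parasympathetic denominator. A ratio of that kind responds to both branches, so analysing it as sympathetic outflow gives it a meaning that the band definitions do not support. HF/total power has the reverse problem, because its denominator contains a band that is partly sympathetic.

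At stake is any branch-specific statement drawn from these ratios. Sympathetic activation is part of the rationale: the surrogate-measures text in Section IV.B says "IR states are accompanied by SNS activation and considerable evidence supports this as a contributor to CVD risk". Section IV.E names it among the mechanisms to pursue later if neither glucose infusion rate nor the vascular measures change, and expects the other outcomes to help direct that work. A rise in LF/HF read as more sympathetic outflow could point the follow-up at the wrong branch. Section IV.F also carries secondary variables into exploratory regressions, where two coupled ratios labelled as different branches would be hard to interpret.

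**Working it through.** The plan gives no power, effect size or band power for heart rate variability, so there is no figure to reproduce. The check is algebraic and uses the band meanings in IV.D. A numerical illustration on stated assumptions follows.

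**Setting up.** Let S be sympathetic and P parasympathetic outflow. A simple linear reading of the definitions is

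HF = c·P and LF = a·S + b·P.

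**LF/HF.** LF/HF = (a·S + b·P)/(c·P) = (a/c)·(S/P) + b/c.

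- With S fixed, the ratio rises when P falls, whenever a·S > 0.
- If a = 0 it does not respond to P, but then it holds no sympathetic information either.
- If S and P rise by the same proportion, S/P is constant and LF/HF does not move, so a real sympathetic rise would be missed.

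**HF/total power.** HF/total = c·P/(c·P + a·S + b·P + VLF), with the VLF term present only if VLF counts in total power. With P fixed, the ratio falls when S rises, although HF itself has not changed.

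**Overlap of the two.** If total power is LF + HF, then HF/total = HF/(LF + HF) = 1/(1 + LF/HF). For each recording one index fixes the other exactly. With VLF included they are no longer identical but remain coupled.

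**Illustration.** These assumptions are not in the documents: linear bands, baseline LF = HF = 1, VLF constant at 0 or 1, and w = sympathetic share of LF at baseline. Then HF = P and LF = w·S + (1 − w)·P, with S = P = 1 at baseline.

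Worked case, w = 0.5:

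- P falls to 0.7 with S = 1. LF = 0.5 + 0.35 = 0.85 and LF/HF = 0.85/0.70 = 1.214, a rise of 21.4%. With VLF = 0, HF/total = 0.70/1.55 = 0.452 against 0.500, a fall of 9.7%.
- S rises to 1.3 with P = 1. LF = 0.65 + 0.50 = 1.15. With VLF = 0, HF/total = 1/2.15 = 0.465 against 0.500, a fall of 7.0%, with HF unchanged.

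Percentage changes over the range of w:

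| w | P −30%: LF/HF | P −30%: HF/total, VLF 0 / 1 | S +30%: HF/total, VLF 0 / 1 |
|---|---|---|---|
| 0.10 | +4.3 | −2.1 / −13.6 | −1.5 / −1.0 |
| 0.25 | +10.7 | −5.1 / −15.2 | −3.6 / −2.4 |
| 0.50 | +21.4 | −9.7 / −17.6 | −7.0 / −4.8 |
| 0.75 | +32.1 | −13.8 / −20.0 | −10.1 / −7.0 |
| 1.00 | +42.9 | −17.6 / −22.2 | −13.0 / −9.1 |

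The last row is a limiting case, since the plan says LF is mixed. When both branches rise by 30%, LF/HF changes by 0% in every row.

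**The case against.** The strongest reply is that this is one sentence of shorthand about one secondary outcome. The paragraph itself says LF is mixed, its heading says balance, and power is determined in each band, so the information needed to see which band moved will exist. Section IV.F treats secondary outcomes as supporting the primary ones or as generating hypotheses, and Section IV.E mentions sympathetic activation only as a subject for later work. All of this stands, and it limits the severity.

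A reader might go further and infer that a purely parasympathetic change would be reported as a sympathetic one instead. The documents do not support that. In the illustration a parasympathetic fall also lowers HF/total, in the correct direction (second results column). The true change would be reported, with an unwarranted sympathetic change beside it. Read as balance, the rise in LF/HF would be correct.

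A reader might also infer that normalised HF is invalid and must be dropped. Nothing in the documents shows this: normalising is a choice of index, and a relative share is a legitimate quantity if it is described as one. Nor is a shift in VLF a confusion between branches, since the plan ties VLF to neither. It matters only for what total power means.

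The plan cites standard methods and sends recordings to a core laboratory for analysis and interpretation. Those sources cannot be seen here, and they may define total power. They would not reconcile two adjacent sentences of the protocol. Lastly, heart rate variability is not the only sympathetic-related information: Section IV.A lists catecholamines before each clamp, though as counter-regulatory hormones rather than as a sympathetic index.

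**Conclusion.** The point holds as a minor one. The interpretation given to LF/HF conflicts with the meanings that the same paragraph gives to the bands, and with the balance wording of its heading and of Aim 2. Neither ratio separates the branches.

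The direction of the cross-effect follows from the plan's definitions, provided LF has some sympathetic share. For HF/total it also requires that LF is part of total power. The size cannot be determined from the documents. The range of about 4% to 43% for LF/HF rests on assumed linear bands, an assumed 30% parasympathetic fall and a sympathetic share of LF between 0.10 and 1.0; nothing in the plan suggests that metformin would produce a fall of that size. Glucose infusion rate, flow-mediated dilation and the sample size are untouched.

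**What to change.** In the Sympathetic/parasympathetic balance paragraph of Section IV.D:

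1. Describe LF/HF as an index of sympathovagal balance, and state that no claim about sympathetic outflow will rest on LF/HF alone.
2. Describe HF/total power as a relative share, and define total power, saying whether VLF is included.
3. Report absolute HF power (parasympathetic) and absolute LF power (mixed) beside the two ratios.

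Section IV.A needs no edit, because it names only heart rate variability. The band powers already come from the planned spectral analysis, so no new data or procedures are needed. The cost is a few sentences of text and two more reported quantities. The trial gives up a stand-alone index of sympathetic outflow from heart rate variability.
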